
Exploratory endpoints
	
 • Quality of life (QOL) questionnaires utilizing the European Organization for Research and Treatment of Cancer (EORTC) QLQ-C30 and the lung-specific QLQ-LC13 to be completed at Screening (Visit 1), pre-ablation (Visit 2A), on Day 1 just prior to discharge (Visit 2B), and at all follow-up visits (Visit 3 through Visit 5). • Numeric Pain Rating Scale, to be completed at Screening (Visit 1), pre-ablation (Visit 2A), on Day 1 just prior to discharge (Visit 2B) and at 30 days ± 7 days post-ablation (Visit 3).

Inclusion criteria
	
 1. Signed informed consent. 2. Patients ≥ 18 years old. 3. Performance status 0-2 (Eastern Cooperative Oncology Group classification [ECOG]). 4. Willing to fulfill all follow-up visit requirements. 5. Medically inoperable primary soft tissue lesion of the lung or patient election not to have surgery. (Medically inoperable is defined per the following indicators: post op predictive FEV1 < 40%; DLCO < 40%; hypoxemia or hypercapnia diabetes with end-organ damage; or severe cerebral, cardiovascular, peripheral vascular disease, or chronic heart disease).

	
6. A soft tissue lesion \leq 2 cm in the outer two-thirds of the lung and not closer than 1 cm to the pleura. Lesion size must be measured with at least 2-dimensional (2D) imaging. Only one lesion meeting the inclusion criteria may be treated during the day of ablation (Visit 2A). However, additional primary disease lesions may be present on the day of ablation.
 
(Outer two-thirds of the lung is defined as peripheral beyond the segmental airway, past the segmental bronchi, such that proximal endobronchial soft tissue lesions are avoided; soft tissue lesions should not be contiguous with the pleura).

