10.9 Analyses to be Conducted

Analyses described below will be performed on the pooled set of 40 patients [REDACTED]

Disposition of Study Patients

Patient disposition will be summarized using counts and percentages. The number and percentage of patients completed and discontinued along with the specific reasons for discontinuation will be tabulated by treatment group and in total.

Demographic and Baseline Characteristics

Summary statistics will be provided for patient demographics and pre-operative ablation characteristics.

Primary and Secondary Endpoint Analyses

Device user experience feedback will be collected from the treating physician who will complete the User Experience Survey following each ablation procedure. The questionnaire will focus on procedure workflow and the user's assessment on ease/difficulty of using the device. Summary statistics will be provided for each question.

The number and percentage of patients achieving technical success will be summarized and a 95% confidence interval will be estimated. Technique efficacy, as well as primary and secondary efficacy rates and hospital readmission rates, will be summarized in a similar manner. Local soft tissue lesion recurrence rates will be estimated using the Kaplan-Meier method and 95% confidence intervals will be provided.

The number and percentage of patients experiencing AEs from the start of ablation (Visit 2A) to Visit 3 (the first post-ablation visit) will be summarized by MedDRA preferred term and system organ class. A similar summary will also be provided for device related and procedure related, and all SAEs. Ninety-five percent confidence intervals may be provided for pre-specified adverse events of interest [REDACTED]

[REDACTED]

[REDACTED]

[REDACTED]

[REDACTED]

[REDACTED]

[REDACTED]

[REDACTED]

[REDACTED]

[REDACTED]

[REDACTED]

Similar summaries will also be provided for the entire observation period from the ablation procedure date through 1 year of follow-up.

The EORTC QOL questionnaires and Numeric Pain Rating Scale scores will be summarized with methodology consistent to the recommendations of the specific survey. Additional endpoints will be summarized with descriptive statistics.

Plans for Interim Analysis

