The original study protocol planned to continue study enrollment until 40 subjects were ablated (approximately 20 subjects ablated by interventional pulmonologists and 20 subjects ablated by thoracic surgeons) and completed Visit 3 (30 days \pm 7 days after the first ablation procedure). However, study enrollment was temporarily halted after 10 subjects were enrolled to convene a meeting of the Data Safety Monitoring Board (DSMB) following the death of one subject. While the DSMB recommended that the study could continue enrollment, the decision was made to permanently stop study enrollment and follow the 10 previously-enrolled subjects through the end of the study follow-up period of 1 year post-ablation. As such, this decision impacts several of the analyses originally planned in the study protocol and those changes will be identified in the appropriate sections throughout this SAP.

1 Study Overview

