1.1 Study Objectives

The primary objective of the study was to evaluate the NeuWave Flex Microwave Ablation System in transbronchial ablation procedures for adult subjects with a medically inoperable primary soft tissue lesion, based on the following assessments:

- a. Device user experience survey
- b. Technical success
- c. Technique efficacy

Device user experience was collected from the treating physician who completed the User Experience Survey following each ablation procedure throughout the study, when applicable. The survey focused on procedure workflow and the user's assessment on ease/difficulty of using the device. The device user experience was designed to augment the Product Development Specialist's understanding of the usability of the Flex system and determine which enhancements, if any, are needed.

The secondary objectives were the following:

1. To evaluate safety through the monitoring of device-related and procedure-related adverse events (AEs) and all serious adverse events (SAEs), from start of ablation through 1-year post-ablation.
2. To establish device and procedure effectiveness by following subjects for 1-year post-ablation to ensure completeness and durability of treatment effect, based on standard endpoints in microwave ablation, as follows:
 - a. Primary efficacy rate
 - b. Secondary efficacy rate
 - c. Local soft lesion recurrence

- d. Length of hospital stay, measured from post-ablation to discharge
 - e. Hospital readmission rate.
3. To calculate hospital readmission rate, defined as any readmission to the hospital within 30 days of the first ablation procedure (Visit 2A).

The exploratory objectives were the following:

- 1. To assess the quality of life post microwave ablation of the lung throughout the 1 year \pm 1 month follow-up period.
- 2. To assess the level of pain during the initial 30 days \pm 7 days post-ablation.

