9.7 Additional Endpoint Analyses

Counts and percentages will be provided for subject performance status as measured by the Eastern Cooperative Oncology Group (ECOG) classification at each visit. Summary statistics will be provided for the numeric pain rating scale measurement and hematology parameters at each visit. Pulmonary function tests will be summarized with summary statistics at each visit where they are measured and the change from the Screening visit measurement will also be summarized. Responses to each question of the EORTC QLQ-LC 13 will be summarized at each visit where the questionnaire was administered. Responses to the EORTC QLQ-C 30 will be listed.

Target lesion details including lesion type, lesion sub-type, size (largest and smallest diameter), location, distance from pleura, and shape will be summarized with statistics appropriate for categorical or continuous variables. Non-target lesion data will be listed. Selected information from the ablation procedure (duration of procedure, duration of ablation delivery, type of anesthesia, maximum power applied, and maximum temperature observed) will also be summarized with statistics appropriate for categorical or continuous variables.

Summary statistics will be presented for evaluations made by the independent reviewer for selected fields relating to ablation of the target lesion (largest diameter, smallest diameter, lesion location, distance from pleura, ablation margin, technical success, technique efficacy, and target lesion recurrence at any visit). All other target lesion data and all non-target lesion data from the independent reviewer will be listed.

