Appendix: Table Shells and List of Listings to be Generated

Table shells are provided, below, for all summaries to be generated for this study. Additionally, a list of all listings to be created is provided corresponding to the eCRFs that were used during this study. All fields collected will be listed.

Table 1
Subject Disposition
All Subjects

	Total
Signed Informed Consent	xx
Full Analysis Set	xx (xx.x%)
Completed the Study	xx (xx.x%)
Discontinued from the Study	xx (xx.x%)
Reason for Discontinuation	
Withdrawal of consent	xx (xx.x%)
Surgical	xx (xx.x%)
Adverse Event	xx (xx.x%)
Death	xx (xx.x%)
Lost to Follow-up	xx (xx.x%)
Physician Decision	xx (xx.x%)
Other	xx (xx.x%)

Note: All percentages are based on the number of subjects in the Full Analysis Set as the denominator.

<< Programming note: Only discontinuation reasons actually observed are to be displayed. Full Analysis Set includes all subjects who have a non-missing date of ablation on the Ablation Procedure CRF. >>

Table 2
 Subject Demographics and Vital Signs
 Full Analysis Set

Characteristics	Overall (N = ##)
Race	
White	xx (xx.x%)
Black or African American	xx (xx.x%)
American Indian or Alaska Native	xx (xx.x%)
Native Hawaiian or Other Pacific Islander	xx (xx.x%)
Asian	xx (xx.x%)
Other	xx (xx.x%)
Ethnicity	
Hispanic or Latino	xx (xx.x%)
Not Hispanic or Latino	xx (xx.x%)
Not reported	xx (xx.x%)
Age (years)	
n	xx
Mean	xx.x
Standard Deviation	x.xxx
Median	xx.x
Minimum, Maximum	xx.x, xx.x
Gender	
Male	xx (xx.x%)
Female	xx (xx.x%)
Childbearing Potential	
Of childbearing potential	xx (xx.x%)
Permanently sterilized	xx (xx.x%)
Postmenopausal	xx (xx.x%)
Body Mass Index (kg/m2)	
n	xx
Mean	xx.x
Standard Deviation	x.xxx
Median	xx.x
Minimum, Maximum	xx.x, xx.x

<<< Programming note: Percentages for childbearing potential are based on the number of females in the study. >>>

Table 3
 Protocol Deviations
 Full Analysis Set

Characteristics	Overall (N = ##)
Total Number of Protocol Deviations	xxx
Specific Types of Protocol Deviations [1]	
Informed Consent Process	xx (xx.x%)
Inclusion/Exclusion Criteria	xx (xx.x%)
Study Procedure	xx (xx.x%)
Visit Out of Window	xx (xx.x%)
Other	xx (xx.x%)
Sponsor Assessment of Protocol Deviations [1]	
Minor	xx (xx.x%)
Major	xx (xx.x%)
Number (%) of Subjects With at Least 1 Protocol Deviation [2]	xx (xx.x%)

1. Denominator used is the total number of protocol deviations reported.
2. Denominator used is the total number of subjects in the column header.

Table 4

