Parameter Statistic	Visit 1/ Screening	Visit 2A/ Day 0	Visit 2B/ Day 1	Visit 3/ Day 30
Self-Reported Pain Intensity in the Last 24 Hours				
n	xx	Xx	xx	xx
Mean	xx.x	xx.x	xx.x	xx.x
Standard Deviation	x.xxx	x.xxx	x.xxx	x.xxx
Median	xx.x	xx.x	xx.x	xx.x
Minimum, Maximum	xx.x, xx.x	xx.x, xx.x	xx.x, xx.x	xx.x, xx.x

Note: A pain score of 0 indicates no pain, 5 indicates moderate pain, and 10 indicates worst possible pain.

Table 13
 EORTC QLQ-LC 13
 Full Analysis Set

Characteristics	Visit 1/ Screening (N = ##)	Visit 2A/ Day 0 (N = ##)	Visit 2B/ Day 1 (N = ##)	Visit 3/ Day 30 (N = ##)	Visit 4/ Month 6 (N = ##)	Visit 5/ Month 12 (N = ##)
How much did you cough?						
Not at all	xx (xx.x%)	xx (xx.x%)	xx (xx.x%)	xx (xx.x%)	xx (xx.x%)	xx (xx.x%)
A little	xx (xx.x%)	xx (xx.x%)	xx (xx.x%)	xx (xx.x%)	xx (xx.x%)	xx (xx.x%)
Quite a bit	xx (xx.x%)	xx (xx.x%)	xx (xx.x%)	xx (xx.x%)	xx (xx.x%)	xx (xx.x%)
Very much	xx (xx.x%)	xx (xx.x%)	xx (xx.x%)	xx (xx.x%)	xx (xx.x%)	xx (xx.x%)
No response	xx (xx.x%)	xx (xx.x%)	xx (xx.x%)	xx (xx.x%)	xx (xx.x%)	xx (xx.x%)
Did you cough up blood?						
Not at all	xx (xx.x%)	xx (xx.x%)	xx (xx.x%)	xx (xx.x%)	xx (xx.x%)	xx (xx.x%)
A little	xx (xx.x%)	xx (xx.x%)	xx (xx.x%)	xx (xx.x%)	xx (xx.x%)	xx (xx.x%)
Quite a bit	xx (xx.x%)	xx (xx.x%)	xx (xx.x%)	xx (xx.x%)	xx (xx.x%)	xx (xx.x%)
Very much	xx (xx.x%)	xx (xx.x%)	xx (xx.x%)	xx (xx.x%)	xx (xx.x%)	xx (xx.x%)
No response	xx (xx.x%)	xx (xx.x%)	xx (xx.x%)	xx (xx.x%)	xx (xx.x%)	xx (xx.x%)
Were you short of breath when you rested?						
Were you short of breath when you walked?						
Were you short of breath when you climbed stairs?						
Have you had a sore mouth or tongue?						
Have you had trouble swallowing?						
Have you had tingling hands or feet?						
Have you had hair loss?						
Have you had pain in your chest?						
Have you had pain in your arm or shoulder?						
Have you had pain in other parts of your body?						
Did you take any medication for pain?						
If yes, how much did it help?						

Note: Responses given refer to during the past week.

Table 14
 Adverse Events by System Organ Class and Preferred Term
 Full Analysis Set

System Organ Class	Preferred Term	Overall (N = ##)
Total		xx (xx.x%)
System Organ Class 1	Preferred Term 1	xx (xx.x%)
	Preferred Term 2	xx (xx.x%)
	Preferred Term 3	xx (xx.x%)
System Organ Class 2	Preferred Term 1	xx (xx.x%)
	Preferred Term 2	xx (xx.x%)
System Organ Class 3	Preferred Term 1	xx (xx.x%)
	Preferred Term 2	xx (xx.x%)
	Preferred Term 3	xx (xx.x%)

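### SAP 9.7 only lists the QLQ-C30, although protocol 10.9 plans to summarize the EORTC questionnaires, and it does not flag or explain the change

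*SAP*

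**What the plan says.** **Objective and endpoint.** SAP 1.1 keeps the exploratory objective "To assess the quality of life post microwave ablation of the lung throughout the 1 year" of follow-up. The protocol synopsis defines the matching endpoint as "Quality of life (QOL) questionnaires utilizing the European Organization for Research and Treatment of Cancer (EORTC) QLQ-C30 and the lung-specific QLQ-LC13", completed at Visits 1, 2A, 2B, 3, 4 and 5.

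**Protocol analysis.** Section 10.9 states: "The EORTC QOL questionnaires and Numeric Pain Rating Scale scores will be summarized with methodology consistent to the recommendations of the specific survey".

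**SAP analysis.** Section 9.7 treats the two instruments differently. For the lung module: "Responses to each question of the EORTC QLQ-LC 13 will be summarized at each visit where the questionnaire was administered". For the general instrument: "Responses to the EORTC QLQ-C 30 will be listed".

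**Planned output.** The SAP appendix opens with: "Table shells are provided, below, for all summaries to be generated for this study". Among Tables 1 to 22, the only quality-of-life table is Table 13, for the LC13. The QLQ-C30 appears once, as Listing 16.

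**Declaring changes.** The SAP's opening text says that stopping at 10 subjects affects several planned analyses and that "those changes will be identified in the appropriate sections throughout this SAP".

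**The concern.** A listing prints individual responses; it does not summarize them. For one of the two named instruments, the SAP therefore drops an analysis that the protocol stated, without saying so. A reader of 9.7 cannot tell whether the omission was decided or overlooked.

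At stake is how the retained objective will be reported. The only quality-of-life summary will come from the lung module, and the general instrument contributes nothing in summary form. If a QLQ-C30 result is wanted for the study report, its derivation, its reference visit and its treatment of unanswered items would all have to be chosen after the SAP was fixed.

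**Working it through.** There is no design figure to reproduce. The check compares the texts and counts the outputs.

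**1. Commitment against plan, same subjects**

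| Measure | Protocol 10.9 | SAP 9.7 | Summary table | Listing |
|---|---|---|---|---|
| Pain scale | summarize | summarized by visit | Table 12 | 12 |
| QLQ-LC13 | summarize | each question, by visit | Table 13 | 17 |
| QLQ-C30 | summarize | listed | none | 16 |

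One protocol sentence covers all three rows. The SAP gives two of them a summary. Section 9.7 also summarizes lung function with change from Screening (Table 10) and hematology (Table 11).

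**2. Volume of data without a summary**

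- Inputs: 6 scheduled administrations (protocol synopsis and Table 1); 10 enrolled subjects (SAP opening text and Section 7).
- Ceiling: 6 × 10 = 60 QLQ-C30 forms. The number is smaller if the reported death cut that subject's visits short, which the SAP does not date, or if forms were missed.
- QLQ-C30 summary statistics planned: 0.
- For contrast, Table 13 has 14 questions × 6 visits = 84 by-visit distributions for the LC13.

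**3. Was the change declared?**

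- Section 6 names the planned Per Protocol set and drops it, citing the stop at 10.
- Section 9.4 names the protocol's full survey summary and narrows it, citing sample size.
- Section 9.5 names the planned rates and the Kaplan-Meier analysis, then moves to listings and a simple proportion, citing sample size.
- Section 9.7 mentions neither the protocol plan for the QLQ-C30 nor a reason.

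The clause in SAP 9.1 about recording differences in the study report does not fill this gap. It covers departures of the final analysis from the SAP, not departures of the SAP from the protocol.

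**4. What a summary at this size can offer**

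For a given standard deviation, the standard error of a mean scales as 1/√n. Against the planned 40 subjects, it is √(40/10) = 2 times as large at 10. The summary would be imprecise, to the same degree as the pain, lung-function and hematology means that the SAP keeps.

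**The case against.** The strongest reply is that this is an exploratory endpoint in a study without hypotheses, stopped at a quarter of its target. With 10 subjects, Listing 16 lets a reader follow each person's answers directly. Sections 9.4 and 9.5 also keep some items and list the rest because of sample size, and keeping one questionnaire while listing the other fits that pattern. This stands as a reason for low priority and as a plausible motive. It does not supply the missing statement in 9.7.

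A narrower reply is that the promise to identify changes covers only those caused by the enrollment stop. That is right. But if the stop caused this change, 9.7 should have said so; if it did not, the documents give no reason at all.

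Several stronger readings are tempting and are not supported:

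- *The LC13 item table breaches the protocol.* Section 10.9 defers to the surveys' recommendations, which neither document reproduces. Table 13 is a summary by visit, so on the visible text that commitment is met.
- *The protocol requires scale scores or change from baseline.* For the EORTC questionnaires, 10.9 names neither.
- *The objective cannot be answered, or item counts cannot show a direction.* Table 13 sets ordered response categories across six visits, and the listings show each subject's course.
- *Small numbers cannot be the reason.* Keeping other summaries in the same section weakens that explanation but does not exclude it.

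**Conclusion.** The point holds for the QLQ-C30. The protocol plans a summary, the SAP provides a listing, and 9.7 does not identify or justify the difference. The effect is that one of two named quality-of-life instruments, with at most 60 forms, receives no summary statistic while the one-year objective is retained.

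This rests on two readings: that the plural in protocol 10.9 covers both EORTC instruments, as the endpoint definition indicates, and that the appendix means what it says about containing every summary. It does not depend on the content of any EORTC manual. It has no bearing on the primary endpoints or on safety. Priority is low.

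**What to change.** In SAP 9.7, add one table of QLQ-C30 results by visit with n, mean, standard deviation, median, minimum and maximum, the statistics SAP 9.1 already sets for continuous variables. Derive the results by the survey's recommended method, as protocol 10.9 states, and cite that method. State how unanswered items are handled, in a way that agrees with the no-imputation rule in SAP 9.9.

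Within-subject change from Screening, the reference the SAP already uses for lung function, would be a useful descriptive addition but is not a protocol requirement. Scoring the LC13 is likewise optional. Keep Table 13 and Listings 16 and 17.

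If the sponsor prefers to list only, a sentence or two in 9.7 should say that this departs from protocol 10.9 and why.

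The cost is a little programming for one table from data already collected, and summaries that will be imprecise with at most 10 subjects per visit. The second route costs only the added text.

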9.8 Plans for Interim Analysis

No formal interim analyses were planned or performed for this study outside of the data reviews that were pre-specified per the DSMB charter.

9.9 Handling of Missing Data

All summaries will be performed only on subjects who receive ablation through the flexible probe. There will be no imputation of data for early terminated subjects or for missing data within the database.

9.10 Sensitivity Analyses

No sensitivity analyses were planned per the study protocol given the absence of any hypotheses to be tested in this descriptive study and none will be performed.

9.11 Subgroup Analysis

No subgroup analyses are planned for this study.

9.12 Assessment of Site Homogeneity

No summaries or adjustments by study site are planned for this study.

Appendix: Table Shells and List of Listings to be Generated

Table shells are provided, below, for all summaries to be generated for this study. Additionally, a list of all listings to be created is provided corresponding to the eCRFs that were used during this study. All fields collected will be listed.

Table 1
Subject Disposition
All Subjects

	Total
Signed Informed Consent	xx
Full Analysis Set	xx (xx.x%)
Completed the Study	xx (xx.x%)
Discontinued from the Study	xx (xx.x%)
Reason for Discontinuation	
Withdrawal of consent	xx (xx.x%)
Surgical	xx (xx.x%)
Adverse Event	xx (xx.x%)
Death	xx (xx.x%)
Lost to Follow-up	xx (xx.x%)
Physician Decision	xx (xx.x%)
Other	xx (xx.x%)

Note: All percentages are based on the number of subjects in the Full Analysis Set as the denominator.

<< Programming note: Only discontinuation reasons actually observed are to be displayed. Full Analysis Set includes all subjects who have a non-missing date of ablation on the Ablation Procedure CRF. >>

Table 2
 Subject Demographics and Vital Signs
 Full Analysis Set

Characteristics	Overall (N = ##)
Race	
White	xx (xx.x%)
Black or African American	xx (xx.x%)
American Indian or Alaska Native	xx (xx.x%)
Native Hawaiian or Other Pacific Islander	xx (xx.x%)
Asian	xx (xx.x%)
Other	xx (xx.x%)
Ethnicity	
Hispanic or Latino	xx (xx.x%)
Not Hispanic or Latino	xx (xx.x%)
Not reported	xx (xx.x%)
Age (years)	
n	xx
Mean	xx.x
Standard Deviation	x.xxx
Median	xx.x
Minimum, Maximum	xx.x, xx.x
Gender	
Male	xx (xx.x%)
Female	xx (xx.x%)
Childbearing Potential	
Of childbearing potential	xx (xx.x%)
Permanently sterilized	xx (xx.x%)
Postmenopausal	xx (xx.x%)
Body Mass Index (kg/m2)	
n	xx
Mean	xx.x
Standard Deviation	x.xxx
Median	xx.x
Minimum, Maximum	xx.x, xx.x

<<< Programming note: Percentages for childbearing potential are based on the number of females in the study. >>>

Table 3
 Protocol Deviations
 Full Analysis Set

Characteristics	Overall (N = ##)
Total Number of Protocol Deviations	xxx
Specific Types of Protocol Deviations [1]	
Informed Consent Process	xx (xx.x%)
Inclusion/Exclusion Criteria	xx (xx.x%)
Study Procedure	xx (xx.x%)
Visit Out of Window	xx (xx.x%)
Other	xx (xx.x%)
Sponsor Assessment of Protocol Deviations [1]	
Minor	xx (xx.x%)
Major	xx (xx.x%)
Number (%) of Subjects With at Least 1 Protocol Deviation [2]	xx (xx.x%)

1. Denominator used is the total number of protocol deviations reported.
2. Denominator used is the total number of subjects in the column header.

Table 4
 Medical History by System Organ Class and Preferred Term
 Full Analysis Set

System Organ Class	Preferred Term	Overall (N = ##)
Total		xx (xx.x%)
System Organ Class 1	Preferred Term 1	xx (xx.x%)
	Preferred Term 2	xx (xx.x%)
	Preferred Term 3	xx (xx.x%)
System Organ Class 2	Preferred Term 1	xx (xx.x%)
	Preferred Term 2	xx (xx.x%)
System Organ Class 3	Preferred Term 1	xx (xx.x%)
	Preferred Term 2	xx (xx.x%)
	Preferred Term 3	xx (xx.x%)
System Organ Class 4	Preferred Term 1	xx (xx.x%)
	Preferred Term 2	xx (xx.x%)

Table 5
 ECOG Performance Status Over Time
 Full Analysis Set

ECOG Score	Visit 1/ Screening	Visit 2A/ Day 0	Visit 3/ Day 30	Visit 4/ Month 6	Visit 5/ Month 12
0 – Fully active	xx (xx.x%)	xx (xx.x%)	xx (xx.x%)	xx (xx.x%)	xx (xx.x%)
1 – Restricted in physically strenuous activity	xx (xx.x%)	xx (xx.x%)	xx (xx.x%)	xx (xx.x%)	xx (xx.x%)
2 – Ambulatory, capable of self care, unable to work	xx (xx.x%)	xx (xx.x%)	xx (xx.x%)	xx (xx.x%)	xx (xx.x%)
3 – Capable of only limited self care	xx (xx.x%)	xx (xx.x%)	xx (xx.x%)	xx (xx.x%)	xx (xx.x%)
4 – Completely disabled	xx (xx.x%)	xx (xx.x%)	xx (xx.x%)	xx (xx.x%)	xx (xx.x%)

<<< Programming note: The number of observed responses at each time point are summarized. No imputation will be performed for subjects not responding at a given visit. >>>

Table 6
 Target Lesion Details – Visit 2A/Day 0
 Full Analysis Set

Characteristics	Overall (N = ##)
Lesion Type	
NSCLC medically inoperable	xx (xx.x%)
NSCLC medically operable; declined surgery	xx (xx.x%)
Other	xx (xx.x%)
Lesion Sub-type	
Squamous cell carcinoma	xx (xx.x%)
Adenocarcinoma	xx (xx.x%)
Large cell carcinoma	xx (xx.x%)
Other	xx (xx.x%)
Lesion Location	
RUL	xx (xx.x%)
RML	xx (xx.x%)
RLL	xx (xx.x%)
LUL	xx (xx.x%)
LLL	xx (xx.x%)
Other	xx (xx.x%)
Lesion Shape	
Sphere	xx (xx.x%)
Ellipse	xx (xx.x%)
Triangular	xx (xx.x%)
Multilobar	xx (xx.x%)
Other	xx (xx.x%)
Distance from Pleura (cm)	
n	xx
Mean	xx.x
Standard Deviation	x.xxx
Median	xx.x
Minimum, Maximum	xx.x, xx.x
Largest Diameter (cm)	
n	xx
Mean	xx.x
Standard Deviation	x.xxx
Median	xx.x
Minimum, Maximum	xx.x, xx.x

Table 6
Target Lesion Details – Visit 2A/Day 0
Full Analysis Set

Characteristics	Overall (N = ##)
Smallest Diameter (cm)	
n	xx
Mean	xx.x
Standard Deviation	x.xxx
Median	xx.x
Minimum, Maximum	xx.x, xx.x
Technical Success	
Yes	xx (xx.x%)
95% Exact Confidence Interval	xx.x%, xx.x%

Table 7
 Ablation Procedure Details
 Full Analysis Set

Characteristics	Overall (N = ##)
Type of Anesthesia	
General	xx (xx.x%)
Conscious sedation	xx (xx.x%)
Deep conscious sedation	xx (xx.x%)
Maximum Power Applied (watts)	
n	xx
Mean	xx.x
Standard Deviation	x.xxx
Median	xx.x
Minimum, Maximum	xx.x, xx.x
Maximum Temperature Observed (Celsius)	
n	xx
Mean	xx.x
Standard Deviation	x.xxx
Median	xx.x
Minimum, Maximum	xx.x, xx.x
Duration of Procedure (minutes)	
n	xx
Mean	xx.x
Standard Deviation	x.xxx
Median	xx.x
Minimum, Maximum	xx.x, xx.x
Duration of Ablation Delivery (minutes)	
n	xx
Mean	xx.x
Standard Deviation	x.xxx
Median	xx.x
Minimum, Maximum	xx.x, xx.x
Device Used	
Flex 6 Probe	xx (xx.x%)
Flex 4 Probe	xx (xx.x%)

Table 7
Ablation Procedure Details
Full Analysis Set

Characteristics	Overall (N = ##)
Final Ablation Zone, smallest diameter (cm)	
n	xx
Mean	xx.x
Standard Deviation	x.xxx
Median	xx.x
Minimum, Maximum	xx.x, xx.x
Total Number of Probe Repositions	
n	xx
Mean	xx.x
Standard Deviation	x.xxx
Median	xx.x
Minimum, Maximum	xx.x, xx.x

Table 8
Technique Efficacy and Target Lesion Recurrence
Full Analysis Set

Characteristics	Overall (N = ##)
Technique Efficacy at Day 30	
Yes	xx (xx.x%)
95% Exact Confidence Interval	xx.x%, xx.x%
Target Lesion Recurrence Day 30 Through Month 12	
Yes	xx (xx.x%)
95% Exact Confidence Interval	xx.x%, xx.x%

Table 9
 User Experience Survey
 Full Analysis Set

Characteristics	Overall (N = ##)
Able to Pass Flex Probe through EWC as Expected	
Yes	xx (xx.x%)
No	xx (xx.x%)
Time to Place Probe in Acceptable Position (minutes)	
n	xx
Mean	xx.x
Standard Deviation	x.xxx
Median	xx.x
Minimum, Maximum	xx.x, xx.x
Number of 3D Scans for Probe Placement	
n	xx
Mean	xx.x
Standard Deviation	x.xxx
Median	xx.x
Minimum, Maximum	xx.x, xx.x
Distance From Probe to Center of Lesion (mm)	
n	xx
Mean	xx.x
Standard Deviation	x.xxx
Median	xx.x
Minimum, Maximum	xx.x, xx.x
Probe Repositioned After Initial Ablation for More Ablation	
Yes	xx (xx.x%)
No	xx (xx.x%)
Performing Ablation With NeuWave Flex System is Predictable	
1 – Disagree	xx (xx.x%)
2	xx (xx.x%)
3	xx (xx.x%)
4	xx (xx.x%)
5 - Agree	xx (xx.x%)

Table 9
 User Experience Survey
 Full Analysis Set

Characteristics	Overall (N = ##)
Ablation With NeuWave Flex System is Simple to Use	
1 – Disagree	xx (xx.x%)
2	xx (xx.x%)
3	xx (xx.x%)
4	xx (xx.x%)
5 - Agree	xx (xx.x%)
Technical Success can be Achieved Similar to a Percutaneous Approach	
1 – Disagree	xx (xx.x%)
2	xx (xx.x%)
3	xx (xx.x%)
4	xx (xx.x%)
5 - Agree	xx (xx.x%)
Confidently Locate the Probe and Targeted Lesion Using my Imaging Tools	
1 – Disagree	xx (xx.x%)
2	xx (xx.x%)
3	xx (xx.x%)
4	xx (xx.x%)
5 - Agree	xx (xx.x%)
Confidently Locate the Ablation Zone Created During Flex Ablation Procedure	
1 – Disagree	xx (xx.x%)
2	xx (xx.x%)
3	xx (xx.x%)
4	xx (xx.x%)
5 – Agree	xx (xx.x%)

Table 10
 Pulmonary Function Tests and Change From Screening Over Time
 Full Analysis Set

Parameter Statistic	Visit 1/ Screening	Visit 4/ Month 6	Change From Visit 1 to Visit 4	Visit 5/ Month 12	Change From Visit 1 to Visit 5
FeNO (ppb)					
n	xx	xx	xx	xx	xx
Mean	xx.x	xx.x	xx.x	xx.x	xx.x
Standard Deviation	x.xxx	x.xxx	x.xxx	x.xxx	x.xxx
Median	xx.x	xx.x	xx.x	xx.x	xx.x
Minimum, Maximum	xx.x, xx.x	xx.x, xx.x	xx.x, xx.x	xx.x, xx.x	xx.x, xx.x
DLCO (mL/min/mmHg)					
n	xx	xx	xx	xx	xx
Mean	xx.x	xx.x	xx.x	xx.x	xx.x
Standard Deviation	x.xxx	x.xxx	x.xxx	x.xxx	x.xxx
Median	xx.x	xx.x	xx.x	xx.x	xx.x
Minimum, Maximum	xx.x, xx.x	xx.x, xx.x	xx.x, xx.x	xx.x, xx.x	xx.x, xx.x
DLCO (%)					
SpO2 (%)					
FVC (mL)					
FVC (%)					
FEV1 (mL)					
FEV1 (% of predicted)					
FEV1/FVC (% of predicted)					
Plethysmographic TLC (mL)					
Plethysmographic TLC (% of predicted)					
Plethysmographic FRC (mL)					
Plethysmographic FRC (% of predicted)					
Gas Dilution TLC (mL)					
Gas Dilution TLC (% of predicted)					
Gas Dilution FRC (mL)					
Gas Dilution FRC (% of predicted)					

<<< Programming note: The number of observed responses at each time point are summarized. No imputation will be performed for subjects not responding at a given visit. >>>

Table 11
 Hematology Tests Over Time
 Full Analysis Set

Parameter Statistic	Visit 1/ Screening	Visit 3/ Day 30	Visit 4/ Month 6	Visit 5/ Month 12
RBC (M/uL)				
n	xx	xx	xx	xx
Mean	xx.x	xx.x	xx.x	xx.x
Standard Deviation	x.xxx	x.xxx	x.xxx	x.xxx
Median	xx.x	xx.x	xx.x	xx.x
Minimum, Maximum	xx.x, xx.x	xx.x, xx.x	xx.x, xx.x	xx.x, xx.x
WBC (K/uL)				
n	xx	xx	xx	xx
Mean	xx.x	xx.x	xx.x	xx.x
Standard Deviation	x.xxx	x.xxx	x.xxx	x.xxx
Median	xx.x	xx.x	xx.x	xx.x
Minimum, Maximum	xx.x, xx.x	xx.x, xx.x	xx.x, xx.x	xx.x, xx.x
Neutrophils (%)				
Lymphocytes (%)				
Monocytes (%)				
Eosinophils (%)				
Basophils (%)				
Hemoglobin (g/dL)				
Hematocrit (%)				
Mean Corpuscular Volume (fL)				
Platelet Count (K/uL)				
PTA (%)				
APTT (seconds)				
PT (seconds)				
INR (ratio)				

<<< Programming note: The number of observed responses at each time point are summarized. No imputation will be performed for subjects not responding at a given visit. >>>

Table 12
 Numeric Pain Rating Scale Over Time
 Full Analysis Set

Parameter Statistic	Visit 1/ Screening	Visit 2A/ Day 0	Visit 2B/ Day 1	Visit 3/ Day 30
Self-Reported Pain Intensity in the Last 24 Hours				
n	xx	Xx	xx	xx
Mean	xx.x	xx.x	xx.x	xx.x
Standard Deviation	x.xxx	x.xxx	x.xxx	x.xxx
Median	xx.x	xx.x	xx.x	xx.x
Minimum, Maximum	xx.x, xx.x	xx.x, xx.x	xx.x, xx.x	xx.x, xx.x

Note: A pain score of 0 indicates no pain, 5 indicates moderate pain, and 10 indicates worst possible pain.

Table 13
 EORTC QLQ-LC 13
 Full Analysis Set

Characteristics	Visit 1/ Screening (N = ##)	Visit 2A/ Day 0 (N = ##)	Visit 2B/ Day 1 (N = ##)	Visit 3/ Day 30 (N = ##)	Visit 4/ Month 6 (N = ##)	Visit 5/ Month 12 (N = ##)
How much did you cough?						
Not at all	xx (xx.x%)	xx (xx.x%)	xx (xx.x%)	xx (xx.x%)	xx (xx.x%)	xx (xx.x%)
A little	xx (xx.x%)	xx (xx.x%)	xx (xx.x%)	xx (xx.x%)	xx (xx.x%)	xx (xx.x%)
Quite a bit	xx (xx.x%)	xx (xx.x%)	xx (xx.x%)	xx (xx.x%)	xx (xx.x%)	xx (xx.x%)
Very much	xx (xx.x%)	xx (xx.x%)	xx (xx.x%)	xx (xx.x%)	xx (xx.x%)	xx (xx.x%)
No response	xx (xx.x%)	xx (xx.x%)	xx (xx.x%)	xx (xx.x%)	xx (xx.x%)	xx (xx.x%)
Did you cough up blood?						
Not at all	xx (xx.x%)	xx (xx.x%)	xx (xx.x%)	xx (xx.x%)	xx (xx.x%)	xx (xx.x%)
A little	xx (xx.x%)	xx (xx.x%)	xx (xx.x%)	xx (xx.x%)	xx (xx.x%)	xx (xx.x%)
Quite a bit	xx (xx.x%)	xx (xx.x%)	xx (xx.x%)	xx (xx.x%)	xx (xx.x%)	xx (xx.x%)
Very much	xx (xx.x%)	xx (xx.x%)	xx (xx.x%)	xx (xx.x%)	xx (xx.x%)	xx (xx.x%)
No response	xx (xx.x%)	xx (xx.x%)	xx (xx.x%)	xx (xx.x%)	xx (xx.x%)	xx (xx.x%)
Were you short of breath when you rested?						
Were you short of breath when you walked?						
Were you short of breath when you climbed stairs?						
Have you had a sore mouth or tongue?						
Have you had trouble swallowing?						
Have you had tingling hands or feet?						
Have you had hair loss?						
Have you had pain in your chest?						
Have you had pain in your arm or shoulder?						
Have you had pain in other parts of your body?						
Did you take any medication for pain?						
If yes, how much did it help?						

Note: Responses given refer to during the past week.

Table 14
 Adverse Events by System Organ Class and Preferred Term
 Full Analysis Set

System Organ Class	Preferred Term	Overall (N = ##)
Total		xx (xx.x%)
System Organ Class 1	Preferred Term 1	xx (xx.x%)
	Preferred Term 2	xx (xx.x%)
	Preferred Term 3	xx (xx.x%)
System Organ Class 2	Preferred Term 1	xx (xx.x%)
	Preferred Term 2	xx (xx.x%)
System Organ Class 3	Preferred Term 1	xx (xx.x%)
	Preferred Term 2	xx (xx.x%)
	Preferred Term 3	xx (xx.x%)
System Organ Class 4	Preferred Term 1	xx (xx.x%)
	Preferred Term 2	xx (xx.x%)

The following tables will have the same format as Table 14:

Table 15	Serious Adverse Events by System Organ Class and Preferred Term Full Analysis Set
Table 16	Adverse Events Related to the Study Device by System Organ Class and Preferred Term Full Analysis Set
Table 17	Serious Adverse Events Related to the Study Device by System Organ Class and Preferred Term Full Analysis Set
Table 18	Adverse Events Related to the Study Procedure by System Organ Class and Preferred Term Full Analysis Set
Table 19	Serious Adverse Events Related to the Study Procedure by System Organ Class and Preferred Term Full Analysis Set
Table 20	Adverse Events Related to the Study Device Within 30 Days of the Initial Ablation Procedure by System Organ Class and Preferred Term Full Analysis Set
Table 21	Serious Adverse Events Related to the Study Device Within 30 Days of the Initial Ablation Procedure by System Organ Class and Preferred Term Full Analysis Set

Table 22
 Target Lesion Details – Independent Reviewer
 Full Analysis Set

Characteristics	Overall (N = ##)
Lesion Location	
RUL	xx (xx.x%)
RML	xx (xx.x%)
RLL	xx (xx.x%)
LUL	xx (xx.x%)
LLL	xx (xx.x%)
Other	xx (xx.x%)
Distance from Pleura (cm)	
n	xx
Mean	xx.x
Standard Deviation	x.xxx
Median	xx.x
Minimum, Maximum	xx.x, xx.x
Largest Diameter (cm)	
n	xx
Mean	xx.x
Standard Deviation	x.xxx
Median	xx.x
Minimum, Maximum	xx.x, xx.x
Smallest Diameter (cm)	
n	xx
Mean	xx.x
Standard Deviation	x.xxx
Median	xx.x
Minimum, Maximum	xx.x, xx.x
Ablation Margin, Smallest Diameter (cm)	
n	xx
Mean	xx.x
Standard Deviation	x.xxx
Median	xx.x
Minimum, Maximum	xx.x, xx.x

Table 22
Target Lesion Details – Independent Reviewer
Full Analysis Set

Characteristics	Overall (N = ##)
Technical Success – Visit 2A/Day 0	
Yes	xx (xx.x%)
95% Exact Confidence Interval	xx.x%, xx.x%
Technique Efficacy at Day 30	
Yes	xx (xx.x%)
95% Exact Confidence Interval	xx.x%, xx.x%
Target Lesion Recurrence Day 30 to Month 12	
Yes	xx (xx.x%)
95% Exact Confidence Interval	xx.x%, xx.x%

The following listings will be generated for this study:

Listing 1	Inclusion/Exclusion Criteria All Subjects
Listing 2	Inclusion/Exclusion Criteria – Ablation Visit All Subjects
Listing 3	Study Visits All Subjects
Listing 4	Study Visit Details All Subjects
Listing 5	Demographics All Subjects
Listing 6	Pregnancy Test All Subjects
Listing 7	Medical History All Subjects
Listing 8	Surgical History All Subjects
Listing 9	Radiation History All Subjects
Listing 10	Vital Signs All Subjects
Listing 11	ECOG Performance Status All Subjects
Listing 12	Pain Rating Scale (NPRS) All Subjects
Listing 13	Pulmonary Function Tests All Subjects
Listing 14	Hematology All Subjects
Listing 15	Genetic Markers Testing All Subjects

Listing 16	EORTC QLQ-C 30 All Subjects
Listing 17	EORTC QLQ-LC 13 All Subjects
Listing 18	Target Lesion Details All Subjects
Listing 19	Non-Target Lesion Details All Subjects
Listing 20	Target Lesion Details Central Reviewer All Subjects
Listing 21	Non-Target Lesion Details Central Reviewer All Subjects
Listing 22	Ablation Procedure All Subjects
Listing 23	Imaging All Subjects
Listing 24	User Experience Survey All Subjects
Listing 25	Discharge All Subjects
Listing 26	UB-04 All Subjects
Listing 27	Concomitant Procedures All Subjects
Listing 28	Concomitant Medications All Subjects
Listing 29	Adverse Events All Subjects
Listing 30	Protocol Deviations All Subjects
Listing 31	Death All Subjects

Listing 32	Subject Completion/Discontinuation All Subjects
------------	--
